Each SMART Connections group will consist of approximately 15 to 20 YLHIV, and approximately 15 groups in total will be formed. Once a sufficient number of YLHIV have been recruited and randomized to form a group, the group will begin with an initial, in-person group meeting with the group facilitator. Online groups will be formed by local government area to ensure participants are able to travel to this initial meeting.

During this meeting, the participants will have an opportunity to meet one another, possibly for the first time, and the facilitators face-to-face. The intent and design of the intervention will be described and ground rules for participation will be set. Ground rules will be discussed and accepted by the group members, but at a minimum, group members will be advised not to talk about what is discussed in the online group with people outside of the group. A brief activity that highlights confidentiality and the consequences of breaking confidentiality will be implemented. During this meeting, the participants will also receive their study phones and the facilitator will record their contact information (telephone numbers, email addresses and Facebook ID). Those who prefer can use their existing sim card (in the study phone), phone or Facebook ID to participate in the project, as long as they are willing to provide the information to the facilitator to enable them to be enrolled in the group. The facilitator will enroll each participant into the virtual group, and then a demonstration of how to open, log-in, post comments and log-out of the group will be made. Each participant should demonstrate the ability to log in and out to the facilitator. The facilitator will also set conditions and expectations for responding to posts and messages by the facilitator, such as limiting his/her responses to group members to business hours and perhaps certain times of the day. Also, the facilitator will instruct the participants if they need to contact the facilitator individually, to send a message to call back when it is safe to do so without risk of breaking confidentiality and the facilitator will call the person.

For those participants who are randomized to the control arm, they will receive their study phone when they return for their next clinic visit.

Standard of care services

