This study will be a randomized controlled trial (RCT) of the SMART Connections, a socio-behavioral intervention using an online social media platform (Facebook) designed to improve retention in HIV care services. Participants will be randomized to the online intervention group or control group (standard of care).

The hypothesis being tested with this study is:

YLHIV who participate in SMART Connections will be more likely to be retained in HIV care at 6-9 months after enrollment than YLHIV in the control group.

Secondarily, we will also test the role of social support as a potential mediator of the intervention effects on retention in care:

Among YLHIV enrolled in ART services, those in the treatment group who are exposed to SMART Connections will have greater social support and, in turn, will be more likely to be retained in HIV care services at 6-9 months compared to those in the control group.

Sample Size and Sampling Design 111.

Sample size

Our primary outcome is retention in HIV care. We will need to recruit 250 experimental participants and 250 control participants to be able to detect a 0.125 difference in the cumulative probability of retention at 12months (0.45 in the control group and 0.575 in the intervention group), corresponding to a hazard ratio of 0.69, with 80% power and 5% significance level for a two-sided comparison using the log-rank test. These calculations also assumed exponential times to event and a 10% loss to follow-up.

Sampling and recruitment procedures

Eligible participants will be sequentially recruited from patients who attend clinic visits at the study facility until the total sample size has been achieved. Potential participants will be assessed for eligibility and written informed consent will be obtained from each participant prior to enrollment in the study.

Randomization procedures

A randomization manager from FHI 360, who is not otherwise involved in the study, will prepare a computerized randomization list using permuted blocks before the start of the study. These envelopes will be given to study staff in charge of the enrollment process. These staff will open the randomization envelopes and inform the participant which group s/he has been assigned to. Participants will be randomized in a 1:1 ratio to proceed with the study procedures. The master randomization list will be maintained at FHI 360 and will not be available to study staff.

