q226 re=1 if q226=1, q226 re=0 if q226=0 | q226=8 | q226=99

At each timepoint, knowledge will be quantified as follows:

know=sum(q226_re-q240_re)/15*100

Changes in knowledge scores from baseline to endline will be quantified as follows:

```
know_chng=know_el - know_bl
```

Responsiveness to particular questions as well as changes from baseline to midpoint, and midpoint to endline, will also be assessed descriptively.

Time on ART

Time on ART at baseline, art_time_bl, will be created based off of medical record data reporting the date the participant started ART as well as the date the participant conducted their baseline questionnaire.

art time bl =q011(from MRE)-today bl (from BL questionnaire)

V. Analysis of participant characteristics

Data from the baseline questionnaire will be cleaned and analyzed descriptively prior to the second round of data collection. Descriptive statistics including means and frequencies will be generated for all quantitative variables collected at baseline in addition to aggregate scores for multiple items measuring potential outcomes such as ART adherence and self-efficacy, social support, retention in HIV services, HIV-related stigma, depression/anxiety, and substance use. A descriptive summary of participant characteristics will be presented by intervention and control groups at all time points. Participant characteristics will include age, marital/relationship status, education, religious affiliation, employment, and food insecurity/household hunger.

VI. Analysis of Study Objectives

Objective 1.

To test the effect of the intervention on the primary outcome, retention in care, we will report Kaplan-Meier cumulative retention probabilities with 95% confidence intervals and plots by study group. The retention probabilities between the groups will be compared with a logrank test stratified by site with a two-sided alpha = 0.05.

The null hypothesis is:

YLHIV who participate in SMART Connections will have the same likelihood of being retained in HIV care at 270 days as YLHIV in the control group.

The alternative hypothesis is:

YLHIV who participate in SMART Connections will be more likely to be retained in HIV care at 270 days than YLHIV in the control group.

Data will be prepared using the stset command:

```
stset timevar, id(id_str) failure(ltfu_28=1) origin(time -0.01) exit(time
```

270)

Where:

```
timevar - time to failure in days, created variable ret_time_28 defined
above
idvar - participant ID id_str

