Two main assumptions underlie the multiple imputation procedure. First, the data are assumed to be missing at random (MAR). According the SAS User Guide (2003a), for a variable to be MAR, "the probability that an observation is missing can depend on the observed variable values of the individual, but not on the missing variable values of the individual." Although the MAR assumption cannot be verified, since independence from the missing values cannot be estimated, Schafer states that the assumption becomes more plausible as the number of variables included in the imputation model increases (Schafer, 1997). We will assess MAR and verify that there is no reason to think the missing-at-random assumption is violated using the mi misstable patterns command specified for the variables to be included in the multiple imputation. The second assumption is that of multivariate normality. However, according to Schafer (1997), inferences based on multiple imputation can be robust to departures from the assumption if the amount of missing data is not large.

The mi set of commands (mi set, mi impute, and mi estimate) will be used for the multiple imputation procedure. To allow results to be reproducible, a random-number seed will be set. M=10 imputed datasets will be created.

For participants that have complete medical record for the study period (i.e. conservative=1, ltfu 28!=. and ret time 28!=0), we will also descriptively present the following by ITT intervention arm:

- n visits=number of clinic visits attended during the study period
- n missed 28=Number of clinic visits missed by more than 28 days during the study period •
- mean followup mo=Mean months of follow-up time during the study period ٠

Objective 2.

To examine the association between treatment exposure and secondary outcomes of social support, HIV knowledge and treatment literacy, adherence and viral suppression, we will conduct significance testing using two-sided tests, with an alpha of 0.05. To examine the relationship between treatment exposure and social support, a continuous variable, we will conduct a t-test using treatment exposure (group) and change from baseline to endline in social support score (ss avg chng). We will similarly examine the relationship between treatment exposure and HIV knowledge by conducting a t-test using treatment exposure (group) and change from baseline to endline in total knowledge score (know chng).

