For adherence and viral suppression at endline, both of which will be dichotomized, we will conduct chisquare tests. We will also explore associations between treatment exposure and secondary outcomes using multiple linear regression models:

1. Social support

Model:	Multiple Linear Regression
Outcomes:	Change in social support score from baseline to endline (ss_avg_chng, individual sub- scales)
Exposures:	Study group (intervention v. comparison)
Covariates:	Age, sex, education at baseline, depression score at baseline, social isolation score at baseline

2. HIV knowledge/treatment literacy

Multiple Linear Regression Model:

Analysis Plan: Using Social Media to improve ART Retention and Treatment outcomes among youth living with HIV in Nigeria - The Youth SMART study

Outcomes: Change in knowledge score from baseline to endline (know chng)

Study group (intervention v. comparison) Exposures:

Covariates: Age, sex, education at baseline

3. Self-reported adherence

Model:	Multiple Logistic Regression
Outcomes:	Adherence at endline
Exposures:	Study group (intervention v. comparison)
Covariates:	Age, sex, education at baseline, household hunger score at baseline, time on ART at baseline, social support sub-scales, adherence at baseline

4. Viral load

Model:	Multiple Linear Regression
Outcomes:	Viral load at endline
Exposures:	Study group (intervention v. comparison)
Covariates:	Age, sex, education at baseline, household hunger score, adherence, time on ART at baseline, social support sub-scales

We will check that the following assumptions of multiple regression are met:

- Independence of observations (i.e. independence of residuals) ٠
- Linear relationships between dependent variable and each independent variable, and between dependent variable and the independent variables collectively. Method: Scatterplots
- Homoscedasticity variance does not change along line of best fit. Method: Plotting studentized • residuals against unstandardized predicted values
- No multicollinearity. Method: Inspect correlation coefficients and VIF values •
- No significant outliers, highly influential points, etc. Method: Exploratory data analysis
- Normal distribution of residuals. Method: Histogram with normal curve fitted, and normal p-plot of residuals

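### About 15 facilitated online groups exist in the intervention arm only, but the sample size, the primary log-rank and the secondary tests treat all participants as independent

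*SAP*

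**What the plan says.** Randomisation is individual and 1:1. The Protocol (Intervention Description) then states: "Each SMART Connections group will consist of approximately 15 to 20 YLHIV, and approximately 15 groups in total will be formed". Groups are filled after allocation ("Once a sufficient number of YLHIV have been recruited and randomized to form a group") and by geography: "Online groups will be formed by local government area to ensure participants are able to travel to this initial meeting". Controls receive standard of care. Under Standard of care services, in-person support groups are open to eligible youth in both arms.

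The sample size (Protocol, Sample size; SAP section III) is 250 per arm for 12-month retention of 0.45 against 0.575, hazard ratio 0.69, 80% power and a two-sided 5% log-rank test. The only further inputs are these: "These calculations also assumed exponential times to event and a 10% loss to follow-up". No ICC or design effect is listed.

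For the primary outcome, SAP section VI (Objective 1) says: "The retention probabilities between the groups will be compared with a logrank test stratified by site with a two-sided alpha = 0.05". The Stata command takes facility as the stratum and has no term for online group.

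Under Objective 2, social support is compared by t-test "using treatment exposure (group) and change from baseline to endline in social support score", and knowledge is handled the same way. For the binary outcomes: "For adherence and viral suppression at endline, both of which will be dichotomized, we will conduct chisquare tests". The SAP summary table adds a t-test for stigma and a chi-square test for substance use. The assumption list for the multiple regressions includes independence of observations, but it is the only item there without a method. Clustered standard errors appear once, as a possible value of an optional argument of the Objective 3 mediation command, with no cluster variable named.

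**The concern.** The intervention is meant to work through peers and a counsellor in a closed group, so members of one group share much of their exposure. The SAP itself expects delivery to differ: it will describe timeliness, engagement and fidelity by group. If outcomes also differ by group, intervention participants are correlated within groups, and the variance of that arm's result is larger than the tests assume. The standard error of the arm comparison is then too small, and a p-value just under 0.05 is hard to interpret.

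The facility strata do not solve this. They adjust for place in both arms, whereas the online groups are formed by local government area (LGA), most LGAs list more than one facility, and the extra variation has no counterpart among controls.

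**Working it through.** **1. The plan's own figure.** Hazard ratio = ln 0.575 / ln 0.45 = 0.693. Events = 4(1.96 + 0.842)² / (ln 0.693)² ≈ 234. For exponential times and exponential 10% loss, the 12-month event probability in an arm is λ/(λ+γ) × [1 − exp(−(λ+γ))], with λ = −ln(retention) and γ = −ln 0.9. The two-arm mean is 0.4655. N = 234/0.4655 = 503, and power at N = 500 is 79.9%. The stated 500 reproduces, with all participants taken as independent.

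**2. Size of the unadjusted test.** Mean group size m = 250/15 = 16.7. The ICC is assumed. The design effect is DE = 1 + (m − 1) × ICC in the intervention arm and 1 in controls. With equal arms the variance factor is v = (1 + DE)/2, and the true size is 2[1 − Φ(1.96/√v)]. The between-group SD of 270-day retention is √(ICC × 0.554 × 0.446), where 0.554 = 0.45^(270/365).

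| Assumed ICC | DE | v | Size by formula | Size by simulation | Between-group SD |
|---|---|---|---|---|---|
| 0 | 1.00 | 1.00 | 5.0% | 5.0% | 0 |
| 0.01 | 1.16 | 1.08 | 5.9% | 6.0% | 5 points |
| 0.02 | 1.31 | 1.16 | 6.8% | 7.1% | 7 points |
| 0.05 | 1.78 | 1.39 | 9.7% | 10.2% | 11 points |

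The simulation ran the facility-stratified log-rank to 270 days, 50,000 trials per cell. It used the Protocol's illustrative LGA sizes, 15 groups formed within LGA, 15 facility strata, exponential times, 10% per year censoring, and a log-normal group effect on the hazard in the intervention arm only, with no difference between arms in average retention. A separate 12-month simulation with 8 strata and 4,000 runs gave 5.1, 5.5, 6.8 and 10.6%.

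**3. How demanding the last row is.** The planned effect at 270 days is 0.554^0.69 − 0.554 = 0.665 − 0.554 = 0.111. ICC 0.05 therefore needs groups to vary with an SD as large as the whole planned effect while the mean effect is zero.

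**4. Secondary tests.** With 227 per arm (about 10% missing, assumed), simulated size at the four ICCs is 5.0, 5.8, 6.6 and 9.6% for the t-test. For the chi-square test at an assumed prevalence of 0.7 to 0.9 it is 5.0–5.2, 5.7–6.0, 6.5–7.0 and 9.2–9.5%.

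**5. The proposed sensitivity analysis.** A facility-stratified Cox model was simulated with variance clustered on online group, multiplied by J/(J − 1), and a t reference on J − 1 df. For J = 15 the standard error is multiplied by √(15/14) = 1.035 and the critical value is 2.145.

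| Assumed ICC | Size, corrected | Size, uncorrected (normal reference) | Power, corrected Cox v log-rank |
|---|---|---|---|
| 0 | 4.6% | 7.8% | 69 v 71% |
| 0.01 | 4.9% | 8.1% | 66 v 70% |
| 0.02 | 5.3% | 8.6% | 63 v 69% |
| 0.05 | 6.0% | 9.6% | 55 v 67% |

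Power is at hazard ratio 0.69 and 270 days. The 71% at ICC 0 is below 80% because follow-up stops at 270 days, not because of clustering. The log-rank power figures above ICC 0 are at its inflated size.

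**6. What 15 groups can show.** For a binary outcome in 15 groups of 13 to 21, the central 95% range of the simulated ANOVA estimate of the ICC is −0.04 to 0.05 when the true value is 0 and −0.03 to 0.09 when it is 0.02.

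**The case against.** - *Individual randomisation protects the test.* It does if the intervention affects nobody, or affects every group alike. It does not if effects differ between groups around a zero mean. The condition stands and limits the claim.
- *The true size might be read as 10%.* The documents do not support that. They give no ICC, and 0.05 requires the demanding null in step 3. The more defensible 0.01 to 0.02 gives an excess of 1 to 2 points.
- *Controls might be read as wholly ungrouped.* They are ungrouped only with respect to the online groups. The in-person groups in standard of care are open to eligible youth in both arms, so they do not create the one-arm structure, but treating controls as singletons is an approximation.
- *Clustering on online group may not be enough.* This stands. The number of facilitators is not stated. In a continuous-outcome check with 8 assumed facilitators, the group-clustered test had size 6.7% at ICC 0.02 and 8.8% at 0.05.
- *Reporting the ICC would settle the matter.* It would not: step 6 shows that 15 groups cannot separate 0 from about 0.02.
- *The trial should have been larger.* At ICC 0.02 the formula gives 500 × 1.157 ≈ 578, but that rests on an assumed ICC. The Protocol timeline places enrolment in autumn 2018 and the SAP is dated December 2019, so a larger sample is not a useful request.

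**Conclusion.** The point holds in a limited form. The online groups exist in one arm only, and neither the sample size nor any primary or Objective 2 test allows for them. The likely effect is modest: a nominal 5% test with true size of about 6 to 7% at ICC 0.01 to 0.02, about 10% as an upper case at 0.05, and exactly nominal if the ICC is zero. All of this rests on assumed ICCs, about 16.7 participants per group and group effects confined to the intervention arm. A reader might infer that the primary analysis is invalid or should be replaced. The documents do not support that, and the log-rank can stay. What is missing is a prespecified analysis showing whether the conclusion depends on independence. It should be added.

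**What to change.** 1. Record the assigned online group and the facilitator for each intervention participant.
2. Keep the log-rank as the primary test. Prespecify one sensitivity analysis: a facility-stratified Cox model by randomised arm, with cluster-robust variance on online group. Controls and intervention participants never placed in a group enter as singletons. Multiply the variance by J/(J − 1) and use t with J − 1 df, where J is the number of online groups. The correction is necessary: without it the analysis has size 7.8% even at ICC 0.
3. If any facilitator runs more than one group, cluster on facilitator instead, with J the number of facilitators.
4. Use the analogous cluster-robust variance with small-sample df for the Objective 2 comparisons, including stigma and substance use.
5. If a group-level ICC is reported, give its interval and say that 15 groups cannot separate 0 from about 0.02.
6. If the primary and sensitivity analyses disagree at 5%, state that the primary p-value assumes no variation between online groups.

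Cost: a group and facilitator identifier linked to study ID, one added Cox model, and a changed variance for the secondary comparisons. Facilitators enrol each member, and the Objective 4 unit cost already counts those assigned to a group, so the link should be obtainable. The Grytics participant data are anonymous and cannot supply it. The small-cluster factor and t reference may have to be applied by hand to the Cox output. Power is somewhat lower and intervals are about 1.02 to 1.08 times as wide as the unclustered Cox interval at ICC 0 to 0.02. A non-significant sensitivity result alone is therefore weak evidence against the primary result.

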treat(T)
```

where:

M - potential mediator (ss tot chng)

x - pre-treatment variables

italicized components are optional:

```
sims - number of simulations for approximation of parameter uncertainty,
default is 1000
seed - random number seed
vce - standard error specification - robust, cluster clustvar, bootstrap,
or jackknife
level - confidence interval, default 95
```

The average causal mediation effect, direct effects, and total effect are stored in scalars.

We will then conduct a sensitivity analysis to quantify the degree of sequantial ignorability violation as the correlation between the error terms of the mediator and outcome models, and then calculating the true values of the average causal mediation effect for given values of the sensitivity parameter rho. The original findings are deemed sensitive if the true effects are found to vary widely as function of rho.

```
medsens (regress M T x) (regress Y T M x), [sims(integer) seed(integer)
Level(#) graph] mediate(M) treat(T)
```

If any of the variables specified above (including the variables used to create the social support scales) have ≥5% missingness, a multiple imputation model will be run as a secondary analysis. The imputation model will include all variables included in the model as well as those that are theoretically related to the variables being imputed (Chantala & Suchindra; Stuart, 2009; White, 2011): Social isolation, depression, household hunger.

The multiple imputation procedure involves 3 phases (Rubin, 1996; Yuan, 2000):

- 1. The missing data are filled in m times to generate m complete data sets.
- 2. The m complete data sets are analyzed by using standard procedures.

3. The results from the m complete data sets are combined for inference.

The mi set of commands (mi set, mi impute, and mi estimate) will be used for the multiple imputation procedure. To allow results to be reproducible, a random-number seed will be set. M=10 imputed datasets will be created.

We will additionally run a second multiple imputation model to impute the social support sub-scale average scores, rather than the individual items, to assess the extent to which imputation at the variable level and at the score level varies.

Objective 4.

To estimate the total costs for the intervention, we will use FHI 360's intervention costing approach to measure costs of intervention activities. FHI 360's approach classifies activities according to three distinct phases: design/development, preparation for implementation, and implementation. We will concentrate on the second and third phases, because costs of design and development activities are not repeated during scale-up. Costs associated with "preparing for implementation" include training of facilitators and other direct costs of implementation such as printing and field logistics, specifically:

- Facilitator training:
 - o Travel
 - Per diem
 - o Venue rental
 - Printed materials
 - Other training materials
 - o Refreshments
- Other non-training related or pre-implementation costs

Costs of implementation are those associated with carrying out the activity including:

- Monthly facilitator meetings
 - o Transportation reimbursement
 - Refreshments
 - Facilitator stipend
- Equipment
 - Phones for facilitators
 - Airtime/data bundles for facilitators
 - Phones for participants
 - Airtime/data bundles for participants

We will also calculate the unit cost per participant, by dividing the total cost by the number of study participants who were assigned to a Facebook group, as well as the unit cost per participant retained, by dividing the total cost by the number of study participants who were assigned to a Facebook group and were retained in HIV care at endline.

Objective 5.

Participant engagement will be summarized descriptively by session and group using data collected by the Grytics software. We will summarize the number of participants' posts and comments, as well as "likes" and other reactions ("love," "haha," "sad," etc.) to scheduled posts, by intervention session, week, and group. Participant perspectives on intervention content and delivery from structured questionnaires conducted at endline will also be summarized using descriptive analyses including means and frequencies. Qualitative

analysis of in-depth interviews with participants at endline will provide further context and detail about participants' thoughts on the intervention and its usefulness.

Objective 6.

Intervention fidelity will be assessed descriptively by presenting the extent to which facilitators were able to post correct messages, hold scheduled group chats, and conduct other activities as directed in the intervention guide. Data on each facilitator's posts, comments, and other activity will be collected by the Grytics software and will be presented by facilitator, scheduled activity, intervetion group, and session. Facilitators' perspectives on session topics and session-specific activities and the ease of delivering intervention content will be assessed through qualitative analysis of in-depth interviews with facilitators. Similarly, facilitator perspectives on the usefulness of the intervention guide and the time-burden required to deliver the intervention will be assessed through in-depth interviews with facilitators.

Concept/variable	Measures	Source of data	Type of data analysis			
Objective 1: To test the effectiveness of a structured online support group to retention in HIV services among YLHIV.						
Retention in HIV services	Dates of clinic visits during study Questions regarding clinic visits, missed visits, reasons for missing visits	Medical record data Structured questionnaires	Kaplan-Meier cumulative retention probabilities, log- rank test			
Objective 2: To examine the effect of the online support group on social support, HIV knowledge and treatment literacy, and ART adherence among YLHIV.						
Social support	MOS-SSS items	Structured questionnaires	t-test			
HIV knowledge and treatment literacy	HIV knowledge questions	Structured questionnaires	t-test			
ART Adherence	AACTG Adherence Assessment items	Structured questionnaires	Chi square test			
	Viral load	Medical record data				
HIV-related Stigma	12-item stigma scale	Structured questionnaires	t-test			
Substance use	AACTG Adherence Assessment items	Structured questionnaires	Chi square test			
Objective 3 : To test the potential mediating effect of social support on the relationship between the intervention and primary outcome.						
Treatment exposure	Assignment to intervention or control	Based on study assignment	Causal mediation analysis			
Social support	MOS-SSS items	Structured questionnaires				

Retention in HIV services	Questions adapted from AACTG Adherence Assessment items	Structured questionnaires				
		Medical record data				
	Dates of clinic visits during study					
Objective 4. To document the costs of the intervention and calculate the unit cost per YLHIV retained. Intervention costs will also be descriptively compared to the costs of adolescent-focused, in-person support groups in the region.						
Cost to put the intervention in place	Training costs (travel, per diem, venue rental, materials)	Study financial records	Descriptive: unit cost			
Implementation costs	Monthly facilitator meetings (transportation and refreshments)	SIDHAS and study financial records	Descriptive			
	Facilitator stipend					
	Equipment (phones) and supplies (airtime/data bundles)					
Estimated in-person	Facilitator stipend	SIDHAS financial	Descriptive			
support group costs	Venue costs	records				
	Transportation costs for facilitator and participants	In-person support group reports (no individual-level data)				
	Refreshments					
	Equipment/supplies for meetings					
Objective 5 : To document participant engagement and perspectives regarding the content and delivery of the intervention to inform scalability and sustainability.						
Engagement	Number of sessions in which participants actively post comments or reply to comments.	Grytics	Descriptive			
	Number of comments per session.					
Perspectives on content and delivery	Perspectives on topic relevancy, clarity, usefulness.	Structured questionnaires	Descriptive			
	Perspectives on content structure (components of sessions)	IDIs	Qualitative			
Perspectives on content and delivery	tent Perspectives on delivery frequency, facilitator engagement, medium of	Structured questionnaires	Descriptive			
	engagement.	IDIs	Qualitative			
Objective 6 : To document implementation and health care provider and support group facilitator perspectives regarding intervention content and delivery to inform scalability and sustainability.						
Fidelity of implementation	Ability to push out correct messages, hold regularly scheduled group chats as directed in intervention guide.	Grytics	Descriptive			

VII. Additional analyses

We will assess the construct validity of the MOS-SSS and HIV Stigma Scale-12 through confirmatory factor analysis. Both scales have been developed in high-income countries and have been found to have good psychometric properties in other settings.

Step 1. Correlation matrix

For each scale, we will first present a polychoric correlation matrix between all variables included in the scale, looking for medium to high correlations between items (see below), and ideally with few items having correlations smaller than ± 0.1 . We will then use the matrix command to store the correlation matrix.

STATA commands:

polychoric [var names]
matrix r=r(R)

Step 2. Goodness-of-fit

MOS-SSS proposed factor structure:

- Tangible Support (latent construct=TAN)
 - o [q309] Someone to help you if you were confined to bed
 - o [q310] Someone to take you to the doctor if you needed it
 - o [q311] Someone to prepare your meals if you were unable to do it yourself
 - o [q312] Someone to help with daily chores if you were sick
- Emotional/Informational Support (latent construct=EMI)
 - o [q301] Someone you can count on to listen to you when you need to talk
 - o [q302] Someone to give you information to help you understand a situation
 - o [q303] Someone to give you good advice about a crisis (serious problem)
 - o [q304] Someone to confide in or talk to about yourself or your problems
 - o [q305] Someone whose advice you really want
 - o [q306] Someone to share your most private worries and fears with
 - o [q307] Someone to turn to for suggestions about how to deal with a personal problem
 - o [q308] Someone who understands your problems
- Affectionate Support Subscale (latent construct=AFF)
 - o [q313] Someone who shows you love and affection
 - o [q314] Someone to love and make you feel like you belong
 - o [q315] Someone who hugs you
- Positive Social Interaction Subscale (latent construct=POS)
 - o [q316] Someone to play with
 - o [q317] Someone to get together with for relaxation
 - o [q318] Someone to do something enjoyable with

HIV Stigma Scale-12 proposed factor structure:

- Personalized stigma (latent construct=PER)
 - \circ ~ [q214] Some people avoid touching me once they know I have HIV
 - o [q215] People I care about stopped calling after learning I have HIV
 - o [q216] I have lost friends by telling them I have HIV
- Disclosure concerns (latent construct=DIS)
 - o [q217] Telling someone I have HIV is risky

- o [q218] I work hard to keep my HIV a secret
- o [q219] I am very careful who I tell that I have HIV
- Concerns about public attitudes (latent construct=PUB)
 - o [q220] People with HIV are treated like outcasts
 - o [q221] Most people believe a person who has HIV is dirty
 - o [q222] Most people are uncomfortable around someone with HIV
- Negative self-image (latent construct=NEG)
 - o [q223] I feel guilty because I have HIV
 - o [q224] People's attitudes about HIV make me feel worse about myself
 - o [q225] I feel I'm not as good a person as others because I have HIV

We will evaluate the goodness-of-fit of the proposed factor structures using CFI and/or RMSEA. We will report point estimates and confidence intervals and will accept the proposed factor structure if fit statistics are acceptable (CFI \ge 0.9, RMSEA \le .10 or upper bound of RMSEA CI \le .12)⁸.

STATA commands:

```
sem (proposed latent construct and factors here), from($r) stand
estat gof, stats(all)
estat mindices
```

If the fit statistics are not acceptable, we, we will evaluate the model's modification indices to determine whether the factor structure can be revised slightly (for example, adding a path between terms if there is a theoretical or conceptual reason to support doing so). If this approach does not produce a model with acceptable fit statistics, we will conduct an exploratory factor analysis to evaluate alternative factor structures. =Once arriving at a factor structure with acceptable fit statistics, we will assess convergent and discriminant validity by assessing whether the scales are correlated to items that should hold similarities (i.e. social isolation, depression) and not correlated to items that should not (i.e. HIV knowledge). We will assess this descriptively through scatter plots and test these

Secondarily, we will assess the relationship between the scale and the primary outcome. We hypothesize the following:

- MOS-SSS
 - o Positive relationship between change in MOS-SSS score and retention
- HIV Stigma Scale-12
 - Negative relationship between change in HIV Stigma Scale-12 (higher scores indicate higher stigma) and retention

If any of the variables specified above have ≥5% missingness (missing or refused), a multiple imputation model will be run as a secondary analysis. The imputation model will include additional variables that are theoretically related to the variables being imputed (Chantala & Suchindra; Stuart, 2009; White, 2011): Age, sex, education at baseline, depression, social isolation, HIV knowledge/treatment literacy.

Although there is some controversy as to whether to round categorical variables after imputation (Allison, 2005), we will round the values in each variable in order to facilitate interpretation of results and given expected very small proportion of missing data.

The multiple imputation procedure involves 3 phases (Rubin, 1996; Yuan, 2000):

Analysis Plan: Using Social Media to improve ART Retention and Treatment outcomes among youth living with HIV in Nigeria - The Youth SMART study

PHSC #1151489; Version 1.0; December 2019

⁸ RMSEA is a measure of the average of the residual variance and covariance; good models have RMSEA values that are at or less than 0.08. CFI is an index that fall between 0 and 1, with values greater than 0.90 considered to be indicators of good fitting models (Hu et al., 1999.). For the purposes of this analysis we will use slightly less stringent cutoffs.

- 1. The missing data are filled in m times to generate m complete data sets.
- 2. The m complete data sets are analyzed by using standard procedures.
- 3. The results from the m complete data sets are combined for inference.

The miset of commands (mi set, mi impute, and mi estimate) will be used for the multiple imputation procedure. To allow results to be reproducible, a random-number seed will be set. M=10 imputed datasets will be created.

VIII. Qualitative analysis

All qualitative interviews will be audio-recorded and transcribed in English for analysis. For qualitative data from open-ended questions with YLHIV as well as qualitative data from IDIs with YLHIV, applied thematic analysis will be used (Guest, MacQueen, & Namey, 2012). Structural codes will first be applied to the data based on each open-ended question to group responses to the same question across all questionnaire responses. This allows for the generation of structural code reports which show participants' responses to a question. After that, data will be analyzed thematically in an iterative process, drawing on anticipated as well as emerging themes. Using codes derived from the data and from existing literature (if any), a codebook will be developed and used for coding and categorizing of data. Once all the responses have been coded, textual coding reports will be produced. Data reduction techniques will be used to examine codes in detail for sub-themes and patterns across responses. Summary reports will be developed identifying the overall themes related to the study objectives. A qualitative data software program (QSR Nvivo) will be used to organize and prepare the data for analysis.

Bibliography

